3.3.1.2. X-ray Assessments to Evaluate Joints

Some participants (n~40), who consent to participate in an optional substudy, will undergo X-ray assessment of knees, elbows and ankles to assess damage within joints detectable at a radiologic level. X-rays will be acquired according to the SoA. At a minimum, joint images will be reviewed following the Pettersson scale [2]. The overall score and joint level score will be calculated. If the X-ray cannot be performed during the baseline period, it is acceptable to postpone this testing to no later than the Week 4/Visit 6 and baseline will be defined as the assessments during the baseline period or at Week 4/Visit 6. If the baseline X-ray could not be performed before or at the Week 4/Visit 6, the study participant does not need to do the 3 (Visit 17) and 6-year (Visit 20) follow-up X-rays.

3.3.1.3. Magnetic Resonance Imaging (MRI) to Evaluate Joints

Some participants (n~20), who consent to participate in an optional substudy, will undergo magnetic resonance imaging (MRI) exams to assess damage within joints by evaluating soft-

tissue changes and osteochondral changes. The MRI scanning protocol will include acquisition of knees, elbows and ankles. The MRI images will be read centrally and the scores will be based on the extended MRI scale with a final score combining soft-tissue and osteochondral sub-scores to form a total score of joint image from 0-5 (0 to be the best and 5 to be the worst). MRI scans will be acquired according to the SoA. If the MRI can't be performed during the baseline period, it is acceptable to postpone this testing no later than Week 4/Visit 6. If the baseline MRI as part of a substudy could not be performed before or at Week 4/Visit 6, the study participant does not need to do the 3- (Visit 17) and 6- (Visit 20) year follow-up MRIs. Baseline is defined as the assessments during the baseline period or at Week 4/Visit 6.

3.3.2. Additional PRO Assessments

3.3.2.1. Hemophilia Life Impacts Questionnaire (HLIQ)

The Hemophilia Life Impacts Questionnaire (HLIQ) is a 9-item assessment of life impacts associated with living with and treating hemophilia. The HLIQ employs a 'past week' recall period. Four items are assessed on a 5-point, ordinal, verbal rating scale (VRS) scored from 0 to 4, while 4 items are rated such that responding 'yes' branches to a 5-point, ordinal VRS and responding 'no' branches to a reason for not participating in the activity, i.e., due to hemophilia or due to other reasons. One item is assessed on a 4-point, ordinal VRS scored from 0 to 3. Higher scores on the VRS indicate greater impact due to living with or treating hemophilia. HLIQ baseline is the closest evaluation prior to or on the day of PF-06838435 infusion, which is measured during the screening period of Study C0371002.

3.3.2.2. EQ-5D-5L

Developed by the EuroQol Group, the EuroQol, 5 dimensions, 5 levels (EQ-5D-5L) is considered the premier measure of health status used in the assessment of the Quality Adjusted Life Year (QALY). It measures 5 dimensions of health on a 5-point (5L) scale including Mobility, Self-care, Usual activities, Pain/discomfort, and Anxiety/depression. Also included is a visual analog scale (VAS) anchored by worst and best imaginable health on a 0 to 100 scale where participants are asked to indicate where on the scale, they rate their current health.

Each of the 5 dimensions (i.e., 'Mobility', 'Self-care', 'Usual activities', 'Pain/discomfort', and 'Anxiety/depression') in the EQ-5D questionnaire is assessed with 5 levels of perceived problems:

Level 1	No problem
Level 2	Slight problems
Level 3	Moderate problems
Level 4	Severe problems
Level 5	Extreme problems

A health state is defined by the combination of one level from each of the 5 dimensions. There is a total of 3125 possible health states. For example, state 11111 indicates no problems on any of the 5 dimensions, while state 12345 indicates no problem with mobility, slight problems with washing or dressing, moderate problems with doing usual activities, severe pain or discomfort and extreme anxiety or depression.

The Index score (total score) of EQ-5D-5L will be obtained, according to the health state defined by the 5 dimension scores, from the Crosswalk Index value calculator and table lookup document under the corresponding country population. For the CSR, weights under the US population will be used to obtain the Index score.

The number and percentage of participants in each level of the 5 dimensions of health score will be assessed and summarized. The VAS score and the Index score (total score) at each visit will be compared with baseline. Missing data will not be imputed, which means missing individual question responses will lead to missing domain scores and total score. EQ-5D-5L baseline is the closest evaluation prior to or on the day of PF-06838435 infusion, which is measured during the screening period of Study C0371002.

3.3.3. Vector Shedding

Vector shedding of PF-06838435 in plasma, saliva, PMBC, urine, and semen will be assessed until 3 consecutive specimens reach below the limit of detection for the given specimen type. Peak value is defined for each participant as the largest result collected prior to the first set of 3 consecutive negative results. Peak values, time to peak values, and the time to 3 consecutive specimens reaching below the limit of detection for each specimen type will be summarized. For the vector shedding summaries, the date of the first set of three consecutive assessments below the limit of detection will be used as the vector clearance date. Additionally, analyses will separately consider the time to the last of the first set of three consecutive negative results, and time to the last positive prior to the first set of three consecutive negatives showing value below the limit of detection will be used as the vector clearance date. Additionally, saliva, semen, and urine samples for time points from a subset of participants will be analyzed for deoxyribonuclease (DNase)-resistant particles and will be summarized separately.

A subgroup of participants will have more extensive vector shedding analysis performed on their specimens to further characterize the kinetics of vector shedding. The data of this subgroup will be separately presented.

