Vector Shedding Analysis by PCR (CL)		X	X*	Weekly, as needed# Utilize mobile phlebotomy / home health services, as needed										
 
•# Plasma, PBMC, saliva, semen, and urine specimens will be collected at baseline and every week after IP administration until 3 consecutive specimens test negative for the given specimen type.
 
•Semen samples can be collected at home the night before a clinic or mobile phlebotomy/ home health service visit and stored in the participant’s freezer until the clinic or mobile phlebotomy/ home health service visit, with the exception of semen samples collected as part of the optional vector shedding sub-study (see bullet point below)
 
•*Optional Vector Shedding Sub-study: Additional (2 hrs (±30 minutes), 24 hrs (±3 hrs), 72 hrs (±4 hrs) after completion of IP infusion and IV line flush on Day 1) samples (plasma, PBMC, saliva, semen, and urine) will be collected from some participants (n=12) who consent to participate in an optional sub-study. Utilize mobile phlebotomy/ home health services as needed.
 

Any Additional Safety Tests	Ongoing (as needed)												Additional laboratory testing may be conducted as deemed clinically necessary by the investigator to ensure safety of participants.	
Adverse Events	Ongoing (including unscheduled visits)												During the Short-Term Monitoring Period (up to and including 52 weeks post-infusion) all SAEs and AEs (including medically important events) will be collected ( Appendix 3 ).	

Procedures Year 1	Screening Period	Baseline Period	IP Infusion	Week 1-12 (± 2 days)					Week 13-52 (±1 week)					
 
•The following Screening labs should be collected in the absence of residual infused FIX (FIX trough): FIX activity, hemostasis markers, inhibitor testing.
 
•The Screening and Baseline period may be extended, upon consultation with the sponsor’s medical monitor. Reason must be recorded in the source documents. Depending on the length of extension (of either period), the medical monitor may request to have visit procedures repeated.
 
•After determination of eligibility, FIX replacement therapy and IP Infusion will be planned at a time when a routine FIX infusion will occur during the study visit on Day 1.
 

Study Visit	1	2	3	4*	5	6	7	8	9	10	11	12	13	

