5. GENERAL METHODOLOGY AND CONVENTIONS

The primary analysis is planned when 40 participants have completed 15 months of follow up after infusion of PF-06838435. The final analysis will be conducted when all dosed participants have completed the entire study (planned 6 years in duration per participant)/or discontinued. There may be several periodic reviews of data between primary analysis and final analysis for the purpose of publications and regulatory updates, etc.

The planned primary analysis is focused on the data collected during the first 15 months post infusion of PF-06838435. Unless otherwise specified analyses will be performed on the Dosed population and will include available data from the time of infusion (or Week 12 as appropriate) through 15 months post infusion regardless of the length of follow up. The final analysis will analyze extended efficacy and longer-term safety and will be performed once all participants have been followed for 6 years or have otherwise withdrawn from study. The endpoint assessments at the specific time points are listed in the table below.

En	dpoint	Primary analysis Statistical Analysis				
•	Primary	ABR for total bleeds (treated and untreated, from Week 12 to Month 15)				
٠	Secondary	ABR for treated bleeds from Week 12 to Month 15				
		AIR for FIX infusions from Week 12 to Month 15				
		Actual value of FIX:C by study visit and the geometric mean of FIX:C from Week 12 to Month 15				
		FIX consumption, from Week 12 to Month 15				
		Number of bleeding events of specific type from Week 12 to Month 15: spontaneous, traumatic; and untreated bleeding.				
		Frequency of target joint bleeds, from Week 12 to Month 15				
		Percentage of participants without bleeds (total bleeds and treated bleeds) will be summarized from Week 12 to Month 15.				
		HJHS at 12 months post PF-06838435 infusion				
		Haem-A-QoL Physical Health domain and HAL Complex Lower Extremity Activities component score at 12 months post PF-06838435 infusion				

		Short-term safety				
• Exp	oloratory	Haem-A-QoL (domains not previously specified) HAL (scores not previously specified) HLIQ item scores at 12 months EQ-5D-5L index score and visual analog scale at 12 months Correlation of FIX:C between one-stage assays and chromogenic straight assay				
		Vector Shedding Substudy				

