6.3.3. Vector Shedding

Descriptive summaries of shedding vector levels in PBMC, saliva, urine, semen and plasma will be provided, including a summary of peak levels and time to peak levels. If multiple assessments are collected for a study visit, the largest value will be included in the summary as a conservative approach. Number and percentage of participants with BLoQ value at each visit will also be summarized in the table. A mean \pm standard error plot of vector shedding over time will be generated with specimen types differentiated by different color/symbols. In the descriptive summary table and the Mean \pm SE plot, only values with assessments above LLQ will be included. In these tables and figures, results from samples without DNase treatment will be presented. The figures will be presented in log-linear scales.

For a subset of participants in C0371002, samples will also be assessed by DNase digestion method for saliva, semen and urine. For these samples, results from both Dnase-digested and DNase undigested samples will be summarized separately in another table, with columns representing the lab method. Individual plots of vector shedding over time will be generated for all participants in the Dosed population. The plot will be paged by participant and paneled by specimen type, and results from both lab methods will be plotted on the same figure, differentiated by color/symbols. In the individual plot, BLoQ value will be imputed as one half of the LLQ value for plotting purposes. Results from the two methods will be presented side by side in a data listing.

Time to undetectable vector (defined as time to first of three consecutive negative results), time to last of three consecutive negative results, and time to the last positive prior to three consecutive negative will be summarized. The summary table will be generated for the 'Vector Shedding substudy' population and the Dosed population.

Vector Shedding subgroup will have more extensive vector shedding analysis performed on their specimens to further characterize the kinetics of vector shedding. The data of this subgroup will be separately presented.

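### Plasma vector-shedding peak and time to peak are summarised for all dosed participants, but outside the 12-person substudy sampling starts at Week 1, so the timing probably reflects the visit schedule

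*SAP*

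**What the plan says.** SAP section 3.3.3 gives the definition: "Peak value is defined for each participant as the largest result collected prior to the first set of 3 consecutive negative results". It then lists what will be summarised for each specimen type: "Peak values, time to peak values, and the time to 3 consecutive specimens reaching below the limit of detection". Section 6.3.3 covers PBMC, saliva, urine, semen and plasma, "including a summary of peak levels and time to peak levels".

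Neither section limits peak or time to peak to the substudy. Section 6.3.3 names the substudy and Dosed populations for the table of clearance times, but names none for the peak summaries. The default in SAP section 5 therefore applies: "Unless otherwise specified analyses will be performed on the Dosed population". Both shedding sections say that substudy data will be shown on their own. Neither says that substudy participants are left out of the all-participant summary.

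The sampling is set in the Schedule of Activities (protocol section 1.3). For all participants, "specimens will be collected at baseline and every week after IP administration until 3 consecutive specimens test negative for the given specimen type". The Day 1 mark in that row carries an asterisk pointing to the optional substudy (n=12), whose additional samples are taken at "2 hrs (±30 minutes), 24 hrs (±3 hrs), 72 hrs (±4 hrs) after completion of IP infusion". Protocol section 8.5.1 repeats the times and the number.

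**The concern.** A peak and a time to peak can be read as kinetics only if sampling covers the period in which the peak occurs. The vector is given once, intravenously, over about 60 minutes (Schedule of Activities, IP infusion row). The natural expectation for plasma is a maximum at or soon after the end of infusion, followed by decline. A participant first sampled at Week 1 would then have the Week 1 result recorded as the peak and the Week 1 visit date as the time of peak.

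A reader of the Dosed summary would take these figures as the size and timing of the plasma maximum. The level would be too low and the timing would be close to the sampling date whatever the true kinetics. If the 12 substudy participants are in the same table, it also mixes two different quantities: a maximum that can capture the first hours and one that cannot.

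**Working it through.** The documents state no sample size, power or error rate for vector shedding, so there is no planned figure to reproduce. The check has four steps.

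**1. First post-dose sample outside the substudy.** The vector-shedding row lists a baseline sample, a Day 1 entry for the substudy only, and then weekly samples. All participants return on Day 2, but for vital signs. The Schedule of Activities note on Visit 4 (Week 1) includes vector shedding among the required specimens. The first post-dose sample is therefore at Week 1, with the ±2 day window that heads the Week 1 to 12 columns.

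The distance from infusion depends on the day count:
- The SAP equates Week 12 minus 2 days with Day 82, so Week 12 is Day 84 and Week 1 is Day 7. With infusion on Day 1, this is 6 days after infusion, range 4 to 8.
- Counting full weeks gives 7 days, range 5 to 9.
- Together the range is about 4 to 9 days.

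**2. Participants affected.** With 12 in the substudy, the share without earlier samples is (N − 12)/N.
- N = 40 (protocol section 9.2): 28/40 = 70%.
- The protocol allows N to exceed 40. For illustration, N = 50 gives 38/50 = 76%.

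**3. Understatement of the plasma peak.** The documents give no plasma half-life. The following assumes mono-exponential decline after the end of infusion. The ratio of the 2-hour level to the level at day d is 2^((d − 2/24)/half-life).

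| Assumed half-life | Ratio at day 7 | Day-7 level as share of 2-hour level |
|---|---|---|
| 1 day | 2^6.917 ≈ 121 | 0.8% |
| 2 days | 2^3.458 ≈ 11 | 9% |
| 4 days | 2^1.729 ≈ 3.3 | 30% |

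The result is sensitive to both the half-life and the sampling day. With a 4-day half-life and a sample at day 4, the share is 51%. With a 1-day half-life and a sample at day 9, it is 0.2%.

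**4. Time to peak under the same assumption.** Take 2 hours for 12 participants and 7 days for 28.
- Pooled median: 7.0 days.
- Pooled mean: (12 × 2/24 + 28 × 7)/40 = (1 + 196)/40 = 4.9 days.

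Both figures are determined by the visit schedule and the proportion of participants in the substudy.

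**The case against.** The strongest reply is that the SAP defines an observed maximum, the largest result collected, and that this is a valid quantity. The design also provides for early kinetics: the substudy has the early samples, its own analysis population (SAP section 4) and its own presentation. Individual plots over time for the Dosed population would show when sampling began. No two passages contradict each other.

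Most of that stands. The definition is coherent, and the fault lies in the label and in the timing summary. Separate presentation does not repair the Dosed table, however. If substudy participants remain in it, two quantities are pooled. If they are taken out, nobody left has a sample before Week 1. Neither document attaches a caveat.

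Three stronger readings are tempting, and the documents do not support them:
- *That the plasma peak is known to be missed.* The documents never state when plasma peaks. Decline from the end of infusion is a plausible inference from the route and duration of dosing.
- *That peaks in saliva, urine, semen and PBMC are missed in the same way.* The documents say nothing about when these peak. The maximum could fall at or after Week 1, in which case time to peak is only coarsened to a weekly grid. Removing time to peak for all five specimen types could discard valid data.
- *That exposure of contacts would be misjudged.* No passage uses peak level or its timing for an exposure decision. The contraception requirement in protocol section 5.1 depends on consecutive negative samples, that is, on clearance.

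**Conclusion.** The point holds for plasma and is minor. It is certain that non-substudy participants have no scheduled post-dose shedding sample before Week 1 and that the SAP does not restrict the peak summaries. It is an inference that plasma vector declines after the infusion. Given that inference, plasma time to peak is set by the schedule in about 28 of 40 participants, and their plasma peak is understated. The size of the understatement is not known from the documents: about 3.3-fold to 121-fold at day 7 for assumed half-lives of 4 days down to 1 day.

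Vector shedding is a tertiary/exploratory endpoint, analysed descriptively. The primary and key secondary analyses do not depend on it. Time to clearance is not affected either, because weekly sampling supports it.

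**What to change.** Amend SAP sections 3.3.3 and 6.3.3 as follows.

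- **Plasma:** report peak level and time to peak from the Vector Shedding Substudy Analysis Population only. For other dosed participants report *highest observed level from Week 1 onward*, with no time to peak, and do not pool it with the substudy.
- **Saliva, urine, semen and PBMC:** keep summaries for all participants, but show substudy and non-substudy participants separately. Label the latter as observed on a weekly grid from Week 1.
- **Time to clearance:** leave in the Dosed population, as planned.

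The change affects SAP wording and table titles only; no samples or visits are added. The cost is precision: the plasma peak summary would rest on 12 participants instead of about 40.

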Vector Shedding Analysis by PCR (CL)	Weekly, as needed# Utilize mobile phlebotomy/ home health services as needed							
 
• # Plasma, PBMC, saliva, semen, and urine: Specimens will be collected at baseline and every week after IP administration until 3 consecutive specimen test negative for the given specimen type.
 
• Semen samples can be collected at home the night before a clinic or mobile phlebotomy/ home health service visit and stored in the participant's freezer until the clinic or mobile phlebotomy/ home health service visit.
 

Any Additional Safety Tests	Ongoing							Additional laboratory testing may be conducted as deemed clinically necessary by the investigator to ensure safety of participants.
Adverse Events	Ongoing (including unscheduled visits)							During the Long-Term Monitoring Period (Week 53 post-infusion to EOS) the following adverse events will be collected: 
 
• SAEs (including medically important events, Appendix 3).
 
• Non-serious AEs determined to be related to IP by the investigator or where causality is unknown.
 

Concomitant Medications, Surgeries, and Procedures	Ongoing (including unscheduled visits)							During the Long-Term Monitoring Period (Week 53 post-infusion to EOS) the concomitant therapy associated with: 
 
SAEs (including medically important events, Appendix 3)
 
Non-serious AEs determined to be related to IP by the investigator or where causality is unknown.
 
 All procedures and surgeries (including elective surgeries) during the Long-Term Monitoring Period are to be recorded.
Review of the eDiary	Ongoing (including unscheduled visits)							Review the eDiary; ensure appropriate entries, during unscheduled and scheduled visits.
Return eDiary							X	The eDiary will be returned during the Week 312 visit.

Study Site: Site that will screen and follow participant post-infusion of PF-06838435 for the duration of the study.

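### SAP 3.3.3 gives two different vector clearance dates, one in conflict with SAP 6.3.3, and no rule says how participants without three consecutive negatives enter the time summaries

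*SAP*

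**What the plan says.** SAP 3.3.3 uses the term vector clearance date twice. First, "the date of the first set of three consecutive assessments below the limit of detection will be used as the vector clearance date"; it does not say which of the three dates in the set is meant. The next sentence adds that "analyses will separately consider the time to the last of the first set of three consecutive negative results", and goes on to the "time to the last positive prior to the first set of three consecutive negatives showing value below the limit of detection". That sentence closes with the same label: "negatives showing value below the limit of detection will be used as the vector clearance date".

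SAP 6.3.3 gives one definition: "Time to undetectable vector (defined as time to first of three consecutive negative results". It lists two further times as separate summaries: "time to last of three consecutive negative results, and time to the last positive prior to three consecutive negative will be summarized". It does not use the term vector clearance date. The table is to be produced for the Vector Shedding substudy "population and the Dosed population".

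Neither section gives a censoring rule or a time-to-event method. SAP 5.2.3 summarises continuous endpoints by descriptive statistics on observed values. SAP 5.3 rules out imputation unless Section 3 provides for it, and 3.3.3 does not. SAP 5 analyses the Dosed population whatever the length of follow-up.

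**The concern.** Two things need settling. First, a date on which vector was detected cannot also be the date of clearance. As written, a programmer following 3.3.3 and one following 6.3.3 could produce different clearance times from the same data.

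Second, all three planned times are anchored to a first set of three consecutive negatives. A participant who has not reached that set has no value for any of them. If the table is made with plain descriptive statistics, that participant is counted in the Dosed population but contributes nothing to the mean, median or maximum. Those still shedding would be the ones left out.

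Duration of shedding has practical interest because Protocol 5.1 and Appendix 4 tie the contraception restriction to three consecutive negative ejaculate samples. A published duration should have one meaning and should account for those still shedding.

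**Working it through.** The plan states no sample size, power or expected clearance time for shedding, so there is no figure of its own to reproduce.

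**1. Distance between the dates.** Protocol 1.3 schedules samples every week until three consecutive negatives per specimen type. With no missed sample and nominal weekly spacing:

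- last positive to first negative: 7 days;
- first negative to third negative: 2 × 7 = 14 days;
- last positive to third negative: 7 + 14 = 21 days.

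The two dates that 3.3.3 labels as clearance therefore differ by about 1 week if the set is dated by its first negative, and by about 3 weeks if by its third. These are nominal gaps. Visit windows of ±2 days in Weeks 1-12, and the extra substudy samples at 2, 24 and 72 hours, can shorten them.

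**2. Can participants be uncleared at the cut?** The documents allow for it but do not show it.

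- The primary analysis is triggered when 40 participants have 15 months of follow-up (SAP 5).
- Enrolment may exceed 40 (Protocol 9.2), so later participants can enter with shorter follow-up.
- Participants may withdraw at any time (Protocol 7.2).
- The Years 2-6 schedule keeps a shedding row: "Weekly, as needed# Utilize mobile phlebotomy/ home health services as needed".

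**3. Size if some are uncleared.** The share uncleared, f, is not in the documents and is assumed to lie between 0% and 30%. The illustration takes the uncleared to be the slowest fraction f. The clearers-only median is then the true (1 − f)/2 quantile: the 45th percentile at f = 10% and the 40th at f = 20%.

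*Exponential times, true mean 1.* Clearers-only median = −ln(1 − (1 − f)/2); true median = ln 2 = 0.693. Clearers-only mean = (1 − f(1 + T))/(1 − f), with T = −ln f. At f = 10%, the median is −ln(0.55) = 0.598, and 0.598/0.693 = 0.86.

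| f | uncleared, of 40 | median ratio | mean ratio |
|---|---|---|---|
| 0% | 0 | 1.00 | 1.00 |
| 2.5% | 1 | 0.96 | 0.91 |
| 5% | 2 | 0.93 | 0.84 |
| 10% | 4 | 0.86 | 0.74 |
| 20% | 8 | 0.74 | 0.60 |
| 30% | 12 | 0.62 | 0.48 |

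*Lognormal times, log-SD s assumed 0.8 to 1.2.* Median ratio = exp(s × z), where z is the normal quantile at (1 − f)/2.

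- f = 10%: z = −0.126, so exp(−0.126 × 0.8) = 0.90 and exp(−0.126 × 1.2) = 0.86.
- f = 20%: z = −0.253, so exp(−0.253 × 0.8) = 0.82 and exp(−0.253 × 1.2) = 0.74.

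The two models agree closely for the median.

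**The case against.** The case for leaving the plan alone is substantial.

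- **One definition exists.** A reader might infer that clearance has no single definition, or that a shorter figure could be picked for quotation. The documents do not support that. SAP 6.3.3 defines time to undetectable vector once, and all three times are prespecified, named separately and all reported. The second label in 3.3.3 looks like a drafting slip. It is still current text, and 6.3.3 does not cancel it because it never mentions a clearance date.
- **No rule restricts the table to clearers.** A reader might infer that the SAP summarises only participants who have cleared and so does understate the times. No sentence says so; the named populations are the substudy and Dosed sets. Omission of the uncleared follows only from the general observed-data conventions, and matters only if someone is uncleared.
- **Clearance may be complete.** Sampling runs until three negatives, and 15 months allows roughly 65 weekly samples. The Years 2-6 row is conditional and is not evidence of late shedding. The true share could be zero. If participants lack a time because they withdrew or were dosed recently, they need not be the slowest, and the ratios above would not apply exactly.
- **Semen.** Protocol 8.5.1 lets semen collection stop for a participant who can give none over a month. Someone never sampled is not a slow clearer, and censoring does not help. Such participants are simply not assessable.
- **Consequence.** The contraception restriction rests on each participant's own samples, not on a summary median. Per-visit counts below quantification and individual plots, both planned in 6.3.3, partly show who is still shedding.

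These points limit the size and certainty of the problem. They do not remove the conflicting label or supply the missing rule.

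**Conclusion.** The conflict in SAP 3.3.3 is certain on the text: two dates carry the clearance label, nominally 1 to 3 weeks apart, and the last-positive date does not fit 6.3.3. The missing rule for participants without three consecutive negatives is also certain.

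Understatement is conditional. It requires plain descriptive statistics on observed times and at least one uncleared participant at the cut. If all have cleared, the bias is nil. If 10% have not, the reported median would be about 0.86-0.90 of its true value; at 20%, about 0.74-0.82. These figures rest on an assumed share, assumed distributions, and the assumption that the uncleared are the slowest.

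Shedding is a tertiary/exploratory, descriptive endpoint. No hypothesis test, type I error or power is touched. This is a modest correction, worth making because it is cheap.

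**What to change.** In SAP 3.3.3, adopt the 6.3.3 definition (first of three consecutive negatives) as the only clearance date and remove that label from the last-positive date. Keep the last-positive and third-negative times as the named supplementary summaries already planned.

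In SAP 6.3.3, estimate time to clearance per specimen type by Kaplan-Meier, censoring participants without three consecutive negatives at their last sample. Report the median with its 95% CI and the number not cleared. Count participants with no sample of a specimen type, semen in particular, separately as not assessable.

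The cost is a few SAP sentences and one standard procedure per specimen type, with no new data. Reported times may become somewhat longer.
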